1.3.4 Preliminary data on DFO and prevention of acute organ injury in humans

DFO was the first iron chelator approved by the FDA, and thus has the longest track record of both efficacy and safety in humans for the treatment of **chronic** iron overload conditions. DFO is also the only iron chelator that is FDA-approved for the treatment of **acute** iron overload (Table 2), and has

Table 2. Comparison of FDA-approved iron chelators³³

Chelator	Deferoxamine (DFO)	Deferasirox (DFX)	Deferiprone (DFP)
Brand name	Desferal	Exjade, Jadenu	Ferriprox
Year of FDA approval	1968	2005	2011
Route of administration	IV, IM, SC	PO	PO
Indication	Acute and chronic iron overload	Chronic iron overload	Chronic iron overload
Iron-binding affinity (pM)	26.6	22.5	19.9
Adverse effects	GI,* hypotension, ** rash, anaphylaxis	GI,* cytopenias, AKI, liver toxicity	GI,* neutropenia, liver toxicity
Elimination half-life (hrs)	0.28	8-16	1.9
Dosing frequency	Continuous	Once per day	Three times per day
Metabolism	Plasma enzymes	Liver (Glucuronidation)	Liver (Glucuronidation)
Excretion	Urine and feces	Feces (84%), urine (8%)	Urine (75-90%)
Contraindications for renal impairment	eGFR<10: contraindicated	eGFR<40: contraindicated	None

*Gastrointestinal (GI) effects include abdominal discomfort, nausea, vomiting, and diarrhea; **Only observed at very high doses

been investigated as a therapeutic strategy for preventing acute organ injury in multiple clinical contexts (**Table 3**), including AKI, cardiopulmonary bypass surgery, and intracerebral hemorrhage.

Clinical studies of DFO for prevention of AKI

Fraga et al.⁷⁷ investigated the effects of DFO versus placebo on the incidence of AKI in 80 critically ill patients with prolonged hypotension. Although the overall incidence of AKI was similar between groups, DFO-treated patients had a lower incidence of severe AKI, as well as lower mean SCr on hospital discharge compared to placebo-treated patients.

Clinical studies of DFO in patients undergoing cardiopulmonary bypass (CPB) surgery and in patients with ST-elevation myocardial infarction (STEMI)

Several groups studied the effects of DFO in patients undergoing CPB surgery and in patients with STEMI.⁷⁸⁻⁸¹ DFO-treated patients had lower generation of superoxide radicals and plasma markers of oxidative stress compared to placebo-treated patients. One RCT found that DFO-treated patients had higher left ventricular ejection fraction following CPB surgery compared to placebo-treated patients.⁸⁰

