5. STUDY PROCEDURES

5.1 Drugs to be used

We will administer DFO or an equal volume of normal saline as an IV infusion over 12h. DFO will be administered at a total dose of 30 mg/kg (maximum total dose, 6g). The DFO (or normal saline) infusion will begin immediately prior to cardiac surgery (after induction of anesthesia and placement of a central venous catheter) and will be continued intra- and postoperatively for a total of 12h. The rationale for the dose of 30 mg/kg is provided in section 1.4. In preparing the DFO infusion, the research pharmacy at each site will follow similar methods used in prior DFO studies^{80,81} and according to the manufacturer recommendations: the prescribed amount of DFO powder, based on the patient's weight, will be dissolved in sterile water to achieve a concentration of 10%. The solution will then be further diluted in normal saline to achieve a final volume of 240mL to standardize the amount of fluid administered in both study arms. The DFO (or normal saline) will be delivered from the research pharmacy to the operating room by a member of the research pharmacy staff or a clinical research coordinator, and will be administered to the patient by the patient's nurse as a continuous 12h IV infusion through a central venous catheter. The DFO or normal saline infusion will begin immediately after induction of anesthesia and placement of a central venous catheter, which is typically inserted into an internal jugular or subclavian vein in the operating room 1 hour prior to the start of surgery for routine clinical care.

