AF	[‡] Confirmed on a 12-lead ECG or a rhythm strip, confirmed by a healthcare provider, or treated (either medically [e.g., amiodarone] or with electrical cardioversion). Patients with AF at baseline will be excluded.	40%	In animal models, DFO prevents CPB-associated arrhythmias. ⁶⁹ In patients with chronic iron overload from beta-thalassemia major, arrhythmias are an indication for DFO treatment intensification. ⁹⁷
Prolonged ventilation	[‡] Requirement for mechanical ventilation >24h postop.	20%	In animal models, DFO attenuates the severity of mechanical ventilation- and lipopolysaccharide-induced acute lung injury. ^{70, 71}
Sepsis	[‡] Life-threatening organ dysfunction caused by a dysregulated host response to infection (assessed within 7d postop). Organ dysfunction is defined as an acute increase in the total SOFA score ≥ 2 points consequent to the infection.	10%	DFO improves monocyte phagolysosome function in vitro. ⁹⁸ Moreover, DFO improves survival in animal models of sepsis. ^{75, 76, 99}

*Anticipated incidence based on our preliminary data and published literature. [†]Troponin I is less affected by skeletal muscle breakdown than troponin T.¹⁰⁰ [‡]Defined as per the Third International Consensus Definition (Sepsis-3).⁹⁴ Abbreviations: AF, atrial fibrillation/flutter; DFO, deferoxamine; ICH, intracerebral hemorrhage; LVEF, left ventricular ejection fraction; POD, postoperative day; URL, upper reference limit.

We will assess time to liberation from IV vasoactive medications, as well as the Vasoactive-Inotropic Score during the first 24 hours. Finally, we will assess the number of ventilator-, hospital-, and ICU-free days to day 28, as well as all-cause hospital mortality. Patients who die prior to 28 days will be assigned 0 ventilator-, hospital-, and ICU-free days.

Iron and oxidative stress markers

We will assess the effect of DFO on iron and oxidative stress markers, including catalytic iron, total iron, total iron binding capacity, ferritin, hepcidin, F(2)-isoprostane, and myeloperoxidase, each assessed pre- and postoperatively (**Figure 4**).

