7.2 Hypotension

DFO may cause hypotension if infused very rapidly (>15 mg/kg/h). For example, DFO-induced hypotension was initially observed in two of three children with acute iron poisoning who received large doses of IV DFO (ranging from 800-1500mg) administered over 15 minutes.¹⁰⁴ Accordingly, the FDA-recommended infusion rate for IV DFO for acute iron intoxication is to not exceed 15 mg/kg/h. Thus, the DFO dosing regimen in the current study (30 mg/kg over 12h hours, which equates to 2.5 mg/kg/h) is 6-fold lower than the maximum FDA-recommended infusion rate.

Regarding dose, the maximum FDA-approved dose for DFO for acute iron intoxication is 6g/day, or ~86 mg/kg in a 70-kg adult, and doses as high as 150 mg/kg/day for 3 months have been used without toxicity.¹⁰⁵ Thus, the dosing of 30 mg/kg in the current study is far below the maximum FDA-approved dose, and is unlikely to cause hypotension. Supporting this, one study administered DFO as an IV bolus of 500mg over 10 minutes in patients with STEMI.⁸¹ This infusion rate of 50mg/min, despite being more than 15-times higher than the infusion rate in the current study (30 mg/kg over 12h, or ~3 mg/min in a 70-kg individual), did not result in any hypotension. Importantly, hypotension was also not observed in the studies of IV DFO for acute organ injury prevention in humans, summarized in **Table 3**. The largest such study, a phase 2 RCT of DFO at 32 mg/kg per day for 3 days in patients with ICH, found the incidence of hypotension was similar in the DFO-treated patients (1 of 144 [1%]) compared to placebo-treated patients (2 of 147 [1%]).⁸²

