9.3 Safety monitoring and reporting

Overview

The patients in this study will be undergoing high risk surgery and will be critically ill postoperatively. It is therefore expected that they will have a number of unrelated adverse health events during the course of their hospital stay. Therefore, we will limit the scope of our adverse events (AEs) monitoring and reporting to the following AEs of special interest (AESI), which will be assessed by review of electronic medical records: hypersensitivity reactions (including anaphylaxis); hypotension; ARDS; infection/sepsis; and any AE that, in the view of the site PI, is definitely or possibly related to the study drug.

Hypersensitivity reaction

During the 12h study drug infusion, patients will be in the highly monitored setting of the operating room or the cardiothoracic ICU. If a patient develops anaphylaxis or any other serious AE during the study drug infusion that is related or possibly related to the study drug, the infusion will be discontinued

immediately. If a patient develops anaphylaxis, the patient will be treated as per routine clinical care, including IM epinephrine, methylprednisolone, antihistamines, normal saline, albuterol, and other therapies as determined by the clinical team.

Hypotension

Although hypotension has not been reported with the DFO dosing regimen that will be used in the current study, we will monitor the frequency and severity of hypotension in the perioperative period by calculating the vasoactive-inotropic score during the first 24 hours of the study, beginning with the start of the study drug infusion. The vasoactive-inotropic score is a validated method for integrating all vasoactive medications and their doses on an hourly basis into a single measure, and has been used in multiple settings,¹¹¹⁻¹¹³ including CPB surgery.¹¹⁴

ARDS

The incidence of ARDS will be assessed daily during the hospital stay for a maximum of 7 days. ARDS will be defined and its severity categorized according to the Berlin criteria¹¹⁵ as follows:

Berlin Definition of ARDS	
Timing	Within 1 week of a known clinical insult
Chest imaging (chest radiograph or computed tomography)	Bilateral opacities – not fully explained by effusions, lobar/lung collapse, or nodules
Origin of edema	Respiratory failure not fully explained by cardiac failure or fluid overload Need objective assessment (e.g., echocardiography) to exclude hydrostatic edema if no risk factor present

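### The 24 h vasoactive-inotropic score used to monitor hypotension includes about 10.6 h (44%) after deferoxamine has cleared, and no infusion-period comparison is specified

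*Combined protocol and SAP*

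**What the plan says.** Section 9.3, under Hypotension, sets the method as "calculating the vasoactive-inotropic score during the first 24 hours of the study, beginning with the start of the study drug infusion". It describes the score as combining vasoactive drugs and their doses hour by hour into one measure. Section 6.4 lists the same score among the secondary endpoints: "as well as the Vasoactive-Inotropic Score during the first 24 hours". Neither place says whether the hourly values are averaged, summed or reduced to a peak. The peak rule in section 6.5 is written for the biomarkers and is not stated to cover this score.

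On exposure, section 5.1 says that the infusion "will be continued intra- and postoperatively for a total of 12h", starting after induction of anesthesia. Table 2 (section 1.3.4) gives deferoxamine an elimination half-life of 0.28 h. Section 7.2 treats hypotension as an infusion-rate effect: "DFO may cause hypotension if infused very rapidly".

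The score does not stand alone. Section 9.3 also names hypotension as an adverse event of special interest, found by record review, graded by CTCAE v5.0 and judged for relatedness. Section 5.2 collects blood pressure for 7 days.

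**The concern.** The documents describe a possible harm that depends on the drug running in, and the drug runs for 12 h. The one quantitative method given under the Hypotension heading covers twice that time. In most of the second half the drug is gone on the protocol's own half-life, and vasoactive need there would mainly reflect recovery from surgery. Pooling both periods can weaken a between-arm contrast that exists only during exposure.

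At stake is the sensitivity of one measure for a named event of special interest. The primary endpoint is not affected. Because the score is built from hourly doses, the infusion hours can be separated without new data.

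**Working it through.** **Inputs from the documents.** Dose 30 mg/kg over 12 h (5.1); rate limit 15 mg/kg/h (7.2); half-life 0.28 h (Table 2); score window 24 h from infusion start (9.3); 148 per group (6.3, where it is sized for AKI and used here only as a scale).

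**Assumptions, not in the documents.** Washout of five half-lives, with three to ten shown. For the power illustration: equal SDs of the exposed and unexposed parts of the score, and correlation ρ between them from 0 to 1.

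**1. The plan's own figure.** 30/12 = 2.5 mg/kg/h and 15/2.5 = 6. Section 7.2 states "30 mg/kg over 12h hours, which equates to 2.5 mg/kg/h" and a 6-fold margin. Both reproduce.

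**2. Drug-free share of the window.** With m half-lives of washout, the share is (24 − 12 − 0.28m)/24.
- m = 3: 11.16/24 = 46.5%
- m = 5: 10.6/24 = 44.2%
- m = 10: 9.2/24 = 38.3%

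**3. Share of a constant on-drug effect kept in a 24 h mean.** f = (12 + 0.28m)/24.
- Effect ends with the infusion (m = 0): 12/24 = 0.50
- Effect ends after five half-lives: 13.4/24 = 0.56

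**4. Other summaries.** A 24 h total keeps the raw difference but adds off-drug noise, so its standardised effect equals that of the mean. For a 24 h peak, an illustrative simulation used skewed (lognormal) hourly scores and a constant added effect over hours 0-12. The peak kept 1.233/2.0 = 62% of the raw difference when off-drug scores were as high as on-drug scores, and 1.955/2.0 = 98% when they were half as high.

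**5. Illustrative power for a mean.** Choose a 0-12 h difference that gives 80% power: d = (1.960 + 0.842) × √(2/148) = 0.326 SD. The standardised effect kept over 24 h is r = f / √[f² + (1−f)² + 2ρf(1−f)], and power is about Φ(2.802r − 1.960).

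| ρ | r, f = 0.50 | Power | r, f = 0.56 | Power |
|---|---|---|---|---|
| 1 | 0.50 | 29% | 0.56 | 35% |
| 0.5 | 0.58 | 37% | 0.64 | 44% |
| 0 | 0.71 | 51% | 0.78 | 59% |

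If the off-drug SD is half the on-drug SD and the effect ends at 12 h, then r = 0.5/(0.5 + 0.25) = 0.67 at ρ = 1 and 0.5/√(0.25 + 0.0625) = 0.89 at ρ = 0. Power is then 46% and 71%.

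**6. Early discontinuation.** Section 9.3 stops the infusion for a serious, possibly related event, and section 6.6 keeps such patients in the analysis. For a stop at hour 3 (an example), exposure covers (3 + 1.4)/24 = 18% of the window.

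**The case against.** The strongest reply is that the score measures drug doses, and support begun for on-drug hypotension need not end when the plasma level falls. Such support belongs in a 24 h window and would reduce the dilution. This stands, and it is a reason to keep the 24 h score.

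Table 2 also does not say that its half-life applies during bypass or to patients with low eGFR, who are eligible down to 15 ml/min/1.73m². This stands as a caution. With a half-life of 1 h (assumed), 24 − 12 − 5 = 7 h, or 29%, would still be drug-free.

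The infusion hours contain the operation itself, so they are noisy too. Both arms undergo surgery, so this costs precision but does not bias the contrast. In the working above, with non-negative correlation, adding off-drug hours never raises the standardised effect.

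A reader might infer that the safety comparison as a whole is biased toward finding no hypotension. The documents do not support that. Record review, CTCAE grading and a relatedness judgement that uses timing form a separate route, and under section 9.4 the DSMB may see adverse events unblinded. That route has limits: section 9.3 gives no blood-pressure threshold or episode definition for hypotension, although it defines ARDS and sepsis in detail, and relatedness is judged event by event by blinded site investigators. It supplements a between-arm comparison and does not replace one.

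Finally, section 7.2 links hypotension to rates six times the trial's, so any effect may be small. That is an argument for the more sensitive window.

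**Conclusion.** The point holds as a low-cost improvement to the safety analysis. On the protocol's figures and a five-half-life washout, about 44% of the scoring window follows drug clearance (38% to 46.5% over the range shown), and no infusion-period comparison is specified.

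It is tempting to say flatly that an infusion effect is diluted to about half. That needs two things the documents do not state: a 24 h mean, and an effect that ends with clearance. Under both, the difference falls to 50-56%; otherwise the loss is smaller and can be slight for a peak. The fall from 80% power to about 29-59% is an illustration under equal SDs, and it is milder if off-drug scores vary less. The documents give no SD, correlation or effect size for the score, so no single power figure should be attributed to the plan.

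**What to change.** In section 9.3:
- Name the summary of the score: mean and peak.
- Add a between-arm comparison over a fixed 0-12 h window from infusion start, for every treated patient, whether or not the infusion was completed.
- Report hours 12-24 separately. This row would show any support that outlasts the drug, including the short washout after hour 12.
- Keep the 24 h score in sections 9.3 and 6.4.

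A window that ends when the infusion is stopped early should be supportive only. Stopping may be triggered by the event being measured, so the window's length would depend on the outcome and would leave out the support that follows.

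The cost is a sentence or two in section 9.3 and one or two extra table rows from hourly data already calculated. The change should be made before unblinding.

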6.3 Sample size and power

Based on our preliminary data and prior studies,^{37, 38} the anticipated AKI event rate in the placebo group is **50%**. We hypothesize the AKI event rate in the DFO group will be **34%**, an effect size that has been proposed to be reasonable for studies in AKI.^{86, 87} A total of 296 patients ($n=148$ per group) will provide 80% power to detect the above treatment effect, with a two-sided α of 0.05. Enrollment of 330 patients provides a small buffer for potential early withdrawal from the study, which we anticipate will be uncommon due to the nature of the study (inpatient and short duration).

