Oxygenation	
Mild	$\text{PaO}_2/\text{FiO}_2$ 201-300 mm Hg with $\text{PEEP} \geq 5 \text{ cm H}_2\text{O}$
Moderate	$\text{PaO}_2/\text{FiO}_2$ 101-200 mm Hg with $\text{PEEP} \geq 5 \text{ cm H}_2\text{O}$
Severe	$\text{PaO}_2/\text{FiO}_2 \leq 100 \text{ mm Hg}$ with $\text{PEEP} \geq 5 \text{ cm H}_2\text{O}$

Abbreviations: FiO_2 , fraction of inspired oxygen; PaO_2 , partial pressure of arterial oxygen; PEEP , positive end-expiratory pressure

In addition to monitoring the incidence and severity of ARDS, we will also record the frequency of the following respiratory outcomes to further monitor for pulmonary toxicity that may not meet the strict criteria for ARDS:

- Requirement for mechanical ventilation >24h postoperatively
- Ventilator-free days to day 28

Infection/sepsis

We will document all suspected or confirmed infections in the first 7 days or until hospital discharge. Infections will be categorized according to the source (pneumonia, genitourinary, biliary, bacteremia, sternal wound infection, or other) and severity (infection alone, sepsis, or septic shock). Sepsis is defined as life-threatening organ dysfunction caused by a dysregulated host response to infection. Organ dysfunction is defined as an acute increase in the total SOFA score ≥ 2 points consequent to the infection.⁹⁴ Septic shock is defined as sepsis with persistent hypotension requiring vasopressors to maintain mean arterial pressure $\geq 65 \text{ mm Hg}$ and having a serum lactate level $> 2 \text{ mmol/L}$ despite adequate volume resuscitation.⁹⁴

Classifying AESI according to severity and relatedness to the study intervention

For each AESI, site PIs will document the severity and relatedness to the study intervention. Severity of AESIs will be assessed using the Common Terminology Criteria for Adverse Events (CTCAE) v5.0. Relatedness will be categorized as definitely, possibly, or not related to the study intervention, according to the following definitions:

- **Definitely Related:** The adverse event is clearly related to the investigational agent – i.e., an event that follows a reasonable temporal sequence from administration of the study intervention, follows a known or expected response pattern to the suspected intervention, or that is confirmed

by improvement on stopping the exposure and that could not be reasonably explained by the known characteristics of the subject's clinical state.

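### Sepsis is listed as an extrarenal endpoint but is defined by the total SOFA score, so a sepsis difference between arms could partly reflect the AKI difference

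*Combined protocol and SAP*

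**What the plan says.** Section 6.4 lists sepsis, with myocardial injury, atrial fibrillation and prolonged ventilation, under its extrarenal subheading and in Table 5, whose title also calls these endpoints extrarenal. Aim 1 draws the same line between AKI and injury to other organs. Table 5 defines sepsis as "Life-threatening organ dysfunction caused by a dysregulated host response to infection (assessed within 7d postop") and anticipates it in 10% of patients.

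Table 5 and section 9.3 give the same operational rule: "Organ dysfunction is defined as an acute increase in the total SOFA score" of at least "2 points consequent to the infection".

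Section 9.3 also grades each infection by "severity (infection alone, sepsis, or septic shock"). The lowest step on that scale therefore turns on SOFA. The next step adds other criteria: "Septic shock is defined as sepsis with persistent hypotension requiring vasopressors to maintain mean arterial pressure" at a stated level, plus a lactate threshold.

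Two further provisions in 9.3 matter here. Infections are captured whatever the SOFA score: "We will document all suspected or confirmed infections in the first 7 days or until hospital discharge". There is also a second severity scale: "Severity of AESIs will be assessed using the Common Terminology Criteria for Adverse Events (CTCAE) v5.0".

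The primary endpoint (6.1) is AKI by creatinine, urine output or renal replacement therapy. Section 6.5 states the hypothesis that DFO reduces sepsis and tests it with a chi-square comparison of proportions. It contains no analysis of sepsis that leaves the kidney out.

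**The concern.** A total organ-failure score is not restricted to organs other than the kidney. Assume that SOFA here is the standard score with a kidney item. Take two patients with the same infection and the same non-renal SOFA change, of whom one also has a kidney decline attributed to the infection. If that decline supplies the points needed to reach 2, one patient is recorded as sepsis and the other as infection alone. The trial is designed on the expectation that DFO makes kidney injury less common, so this classification may differ between arms for a renal reason.

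What is at stake is interpretation. Table 5 justifies the sepsis endpoint by monocyte function and by survival in animal sepsis models, not by kidney protection. A lower sepsis rate on DFO would be read as support for that extrarenal rationale. As planned, no analysis could show whether the difference remains once the kidney is left out of the score.

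The plan also does not say how the link to the infection is judged, or from what reference time the SOFA rise is counted. Both matter in a population where half the placebo patients are expected to have AKI.

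**Working it through.** **1. The planned AKI effect.** Section 6.3 anticipates AKI in 50% on placebo. For the active arm it says "We hypothesize the AKI event rate in the DFO group will be" 34%. The ratio is 0.34/0.50 = 0.68, a relative reduction of 0.32.

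The plan's own sample size reproduces. With mean proportion 0.42 and pooled variance under the null:

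n = [1.960 × √(2 × 0.42 × 0.58) + 0.842 × √(0.50 × 0.50 + 0.34 × 0.66)]² / 0.16² ≈ 148.2 per group

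That is 149 when rounded up, against 148 stated; power at 148 per group is 79.9%. The 50% and 34% rates are therefore the ones the trial was sized on.

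**2. Where the overlap can act.** The definition requires infection and a SOFA rise consequent to it. A patient contributes to the overlap only if all of these hold: the patient is infected; kidney function worsens; the worsening is attributed to the infection; and the patient would not reach 2 points without it. Call the share of sepsis cases that meet all of these q. The documents give no value for q.

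**3. Illustrative size.** Assume equal infection in both arms, placebo sepsis of 10% (Table 5), and kidney-dependent cases falling by the same 0.32 as AKI overall:

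DFO sepsis = 0.10 × (1 − q × 0.32)

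Section 6.6 targets 300 analyzable patients. At 1:1 allocation this is 150 per arm, so 15 placebo cases are expected. The last column is the chance that the planned chi-square test is significant in favor of DFO (two-sided 0.05, no continuity correction): Φ[(d − 1.960 × s₀)/s₁]. Here d is the difference in proportions, and s₀ and s₁ are its standard errors with pooled and unpooled variance.

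| q (assumed) | DFO sepsis | DFO cases per 150 | Fewer than placebo | Chance of significance |
|---|---|---|---|---|
| 0 | 10.0% | 15.0 | 0 | 2.5% |
| 0.10 | 9.7% | 14.5 | 0.5 | 3.1% |
| 0.30 | 9.0% | 13.6 | 1.4 | 4.7% |
| 0.50 | 8.4% | 12.6 | 2.4 | 6.9% |
| 1 (extreme) | 6.8% | 10.2 | 4.8 | 16.8% |

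Example for q = 0.50: d = 0.016, s₀ = 0.0334, s₁ = 0.0334, so Φ[(0.016 − 0.0654)/0.0334] = Φ(−1.48) = 6.9%.

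**4. Direction.** The ratio 0.68 is planned for AKI of any degree in all patients. The ratio for kidney-dependent sepsis, r, may differ. In general, DFO sepsis = 0.10 × (1 − q × (1 − r)). With r = 1 there is no shift. With r above 1, DFO sepsis exceeds 10%. The latter is possible: if more placebo patients already have surgical AKI when infection begins, their reference SOFA already carries kidney points and they have less room for a further rise.

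**The case against.** The case against has several sound parts.

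- **The SOFA items are not in the documents.** The abbreviation list expands the name and the sepsis definition cites a consensus source, but no items or thresholds are given. That there is a kidney item, and that a change meeting the AKI definition would score 2 points, cannot be checked here. This stands, so the point is stated conditionally. What the documents do show is an endpoint labeled extrarenal and scored on a total with no organ left out.
- **The link to infection is part of the definition.** Surgical AKI without infection, or AKI judged unrelated to it, does not count. This limits the overlap to infected patients, as in step 2. It does not remove the overlap, because the plan states no attribution rule, adjudication or SOFA reference time.
- **The 0.68 is borrowed.** Nothing shows that DFO would cut infection-related kidney dysfunction by the ratio planned for all AKI. This stands; it is an assumption alongside q.
- **The hypothesis in 6.5 does not claim a sepsis benefit independent of AKI.** This is true of its wording. The extrarenal label in 6.4 and the rationale in Table 5 are what invite that reading.

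A reader might go further and infer that less AKI on DFO necessarily lowers recorded sepsis. The documents do not support this, given the attribution condition and the uncertain direction.

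A reader might also infer that the grading could hide an infection harm. That too goes beyond the text. All infections are recorded regardless of SOFA, adverse events of special interest are also graded by CTCAE v5.0, and the DSMB may review adverse events unblinded (9.4). Only the split between infection alone and sepsis, and the septic shock grade that presupposes sepsis, passes through SOFA.

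**Conclusion.** The point holds as a limit on interpretation. As defined, sepsis is not shown to be separate from the renal primary endpoint, and no planned analysis separates them. A sepsis difference could partly reflect the AKI difference.

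The likely size is modest: about 0.5 to 2.4 fewer cases per 150 for q from 10% to 50%, and under 5 in the extreme. The overlap alone would seldom produce a significant result. These figures rest on three assumptions that the documents do not settle: that SOFA has a kidney item, the value of q, and the use of 0.68 for kidney-dependent sepsis. The shift could also run the other way.

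The primary analysis is unaffected. The change is worth making because it decides whether a sepsis result may be called extrarenal, but it is not critical to the trial.

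**What to change.** Keep the stated consensus definition as the sepsis endpoint.

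- **Section 6.5:** add a pre-specified sensitivity analysis of sepsis defined as infection with a rise of at least 2 points in SOFA without the kidney item. Report infection incidence by arm beside both versions. Describe a sepsis effect as extrarenal only if the non-renal version agrees.
- **Section 9.3:** tabulate infection severity with and without the kidney item. State the SOFA reference time and how attribution to the infection is judged, so that both versions are scored the same way in every patient.

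The cost is SAP wording and one derived variable. The data list in 5.2 does not name SOFA or its items, so the sites should record item scores and not only the total. The stated definition already requires the total to be worked out for infected patients.

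The downside is that the non-renal version is not the consensus definition and will have fewer events. It is less precise and remains supportive only.
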